7.1.7 Life-Threatening Adverse Drug Experience

Any adverse event or suspected adverse reaction that places the patient or subject, in the view of the investigator or sponsor, at immediate risk of death from the reaction as it occurred, i.e., it does not include a reaction that had it occurred in a more severe form, might have caused death.

7.1.8 Protocol Deviation (NIH Definition)

Any change, divergence, or departure from the NIH Intramural IRB-approved research protocol.

7.1.9 Non-Compliance (NIH Definition)

The failure to comply with applicable NIH Human Research Protections Program (HRPP) policies, NIH Intramural IRB requirements, or regulatory requirements for the protection of human research subjects.

7.1.10 Unanticipated Problem

Any incident, experience, or outcome that:

- 1. Is unexpected in terms of nature, severity, or frequency in relation to:
 - a. the research risks that are described in the NIH Intramural IRB-approved research protocol and informed consent document; Investigator's Brochure or other study documents, and
 - b. the characteristics of the subject population being studied; AND
- 2. Is related or possibly related to participation in the research; AND
- 3. Suggests that the research places subjects or others at a greater risk of harm (including physical, psychological, economic, or social harm) than was previously known or recognized.

7.2 NIH INTRAMURAL-IRB AND CLINICAL DIRECTOR (CD) REPORTING

7.2.1 NIH Intramural IRB and NCI CD Expedited Reporting of Unanticipated Problems and Deaths

The protocol PI will report in the NIH Problem Form to the NIH Intramural IRB and NCI Clinical Director:

• All deaths, except deaths due to progressive disease

- All protocol deviations
- All unanticipated problems
- All non-compliance

Reports must be received within 7 days of PI awareness via iRIS.

7.2.2 NIH Intramural IRB Requirements for PI Reporting at Continuing Review

The protocol PI will report to the NIH Intramural IRB:

- 1. A summary of all protocol deviations in a tabular format to include the date the deviation occurred, a brief description of the deviation, and any corrective action.
- 2. A summary of any instances of non-compliance.
- 3. A tabular summary of the following adverse events:
 - All grade 2 **unexpected** events that are possibly, probably, or definitely related to the research
 - All grade 3 and 4 events that are possibly, probably, or definitely related to the research
 - All grade 5 events regardless of attribution
 - All serious events regardless of attribution.

Note: Grade 1 events are not required to be reported.

7.2.3 NIH Intramural IRB Reporting of IND Safety Reports

Only IND Safety Reports that meet the definition of an unanticipated problem will need to be reported to the NIH Intramural IRB.

7.3 IND Sponsor Reporting Criteria

From the time the subject receives the investigational agent/intervention to the time of the second follow-up evaluation, the investigator must immediately report to the sponsor, using the mandatory MedWatch Form FDA 3500A or equivalent, any serious adverse event, whether or not considered drug-related, including those listed in the protocol or Investigator's Brochure and must include an assessment of whether there is a reasonable possibility that the drug caused the event. For serious adverse events that occur after the second follow-up evaluation, only those events that have an attribution of at least possibly related to the agent/intervention will be reported.

Required timing for reporting per the above guidelines:

- Deaths (except death due to progressive disease) must be reported via email within 24 hours. A complete report must be submitted within one business day.
- Other serious adverse events as well as deaths due to progressive disease must be reported within one business day.

Events will be submitted to the Center for Cancer Research (CCR) at [contact] and to the CCR PI and study coordinator.

All serious adverse events will be reported by the Sponsor (Center for Cancer Research) as per FDA 21 CFR 312.32.

7.3.1 Reporting Pregnancy

7.3.1.1 Maternal Exposure

If a patient becomes pregnant during study treatment, the treatment should be discontinued immediately. Pregnancies occurring during study treatment and for the first 120 days after the last vaccination should be reported to the Sponsor. The potential risk of exposure of the fetus to the investigational agent should be documented using the MedWatch Form FDA 3500A or equivalent.

Pregnancy itself is not regarded as an SAE. However, as patients who become pregnant on study risk intrauterine exposure of the fetus to agents which may be teratogenic, the CCR is requesting that pregnancy should be reported in an expedited manner as grade 3 "Pregnancy, puerperium and perinatal conditions - Other (pregnancy)" under the Pregnancy, puerperium and perinatal conditions SOC.

Congenital abnormalities or birth defects and spontaneous miscarriages should be reported and handled as SAEs. Elective abortions without complications should not be handled as AEs. The outcome of all pregnancies (spontaneous miscarriage, elective termination, ectopic pregnancy, normal birth, or congenital abnormality) should be followed up and documented.

If any pregnancy occurs in the course of the study, then the investigator should inform the Sponsor within one day, i.e., immediately, but **no later than 24 hours** of when he or she becomes aware of it.

The designated Sponsor representative will work with the investigator to ensure that all relevant information is provided to the Sponsor within 1-5 calendar days for SAEs and within 30 days for all other pregnancies.

The same timelines apply when outcome information is available.

7.3.1.2 Paternal Exposure

Male patients should refrain from fathering a child or donating sperm during the study and for 120 days after the last vaccination.

Pregnancy of the patient's partner is not considered to be an AE. However, the outcome of all pregnancies (spontaneous miscarriage, elective termination, ectopic pregnancy, normal birth, or congenital abnormality) occurring from the date of the first dose until 120 days after the last dose should, if possible, be followed up and documented.

7.4 SAFETY REPORTING CRITERIA TO THE PHARMACEUTICAL COLLABORATOR

The Sponsor (Center for Cancer Research) will provide Moderna with: (1) copies of all safety reports concurrently with their submission to the FDA; (2) a cumulative listing of adverse events (including suspected adverse reactions) on a quarterly basis; (3) notice within 48 hours of case completion with respect to a serious adverse event; and, (4) any other information affecting the safety of human subjects. This information will be submitted to Moderna at [contact].

Note: The quarterly cumulative listing of adverse events (including suspected adverse reactions) will be submitted by the PI/research team to the Sponsor for reporting to Moderna.

7.5 INSTITUTIONAL BIOSAFETY COMMITTEE (IBC) REPORTING CRITERIA

7.5.1 Serious Adverse Event Reports to IBC

The PI (or delegate) will notify IBC of any unexpected fatal or life-threatening experience associated with the use of the gene transfer product as soon as possible but in no event later than 7 calendar days of initial receipt of the information. Serious adverse events that are unexpected and associated with the use of the gene transfer product, but are not fatal or life-threatening, must be reported to the NIH IBC as soon as possible, but not later than 15 calendar days after the investigator's initial receipt of the information. Adverse events may be reported by using the MedWatch Form FDA 3500A or equivalent.

7.5.2 Annual Reports to IBC

Within 60 days after the one-year anniversary of the date on which the IBC approved the initial protocol, and after each subsequent anniversary until the trial is completed, the PI (or delegate) shall submit the information described below. Alternatively, the NIH Intramural IRB continuing review report can be sent to the IBC in lieu of a separate report. Please include the IBC protocol number on the report.

7.5.2.1 Clinical Trial Information

A brief summary of the status of the trial in progress or completed during the previous year. The summary is required to include the following information:

- Title and purpose of the trial
- Clinical site
- Principal Investigator
- Clinical protocol identifiers
- Participant population (such as disease indication and general age group, e.g., adult or pediatric)
- Total number of participants planned for inclusion in the trial; the number entered into the trial to date whose participation in the trial was completed; and the number who dropped out of the trial with a brief description of the reasons
- Status of the trial, e.g., open to accrual of subjects, closed but data collection ongoing, or fully completed
- If the trial has been completed, a brief description of any study results.

7.5.2.2 Progress Report and Data Analysis

Information obtained during the previous year's clinical and non-clinical investigations, including:

• Narrative or tabular summary showing the most frequent and most serious adverse experiences by body system

- Summary of all serious adverse events submitted during the past year
- Summary of serious adverse events that were expected or considered to have causes not associated with the use of the gene transfer product such as disease progression or concurrent medications
- If any deaths have occurred, the number of participants who died during participation in the investigation and causes of death
- Brief description of any information obtained that is pertinent to an understanding of the gene transfer product's actions, including, for example, information about dose-response, information from controlled trials, and information about bioavailability.

7.6 DATA AND SAFETY MONITORING PLAN

7.6.1 Principal Investigator/Research Team

The clinical research team will meet on a weekly basis when patients are being actively treated on the trial to discuss each patient. Decisions about enrollment and dose escalation, if applicable, will be made based on the toxicity data from prior patients.

All data will be collected in a timely manner and reviewed by the PI or AI. Adverse events will be reported as required above. Any safety concerns, new information that might affect either the ethical and/or scientific conduct of the trial, or protocol deviations will be reported to the NIH Intramural IRB using iRIS.

The PI will review AE and response data on each patient to ensure safety and data accuracy. The PI will personally conduct or supervise the investigation and provide appropriate delegation of responsibilities to other members of the research staff.

7.6.2 Sponsor Monitoring Plan

As a Sponsor for clinical trials, FDA regulations require the CCR to maintain a monitoring program. The CCR's program allows for confirmation of: study data, specifically data that could affect the interpretation of primary study endpoints; adherence to the protocol, regulations, and SOPs; and human subject's protection. This is done through independent verification of study data with source documentation focusing on:

- Informed consent process
- Eligibility confirmation
- Drug administration and accountability
- Adverse events monitoring
- Response assessment

The monitoring program also extends to multi-site research when the CCR is the coordinating center.

This trial will be monitored by personnel employed by a CCR contractor. Monitors are qualified by training and experience to monitor the progress of clinical trials. Personnel monitoring this study will not be affiliated in any way with the trial conduct.

7.6.3 Safety Monitoring Committee (SMC)

This protocol will require oversight from the SMC. Initial review will occur as soon as possible after the annual NIH Intramural IRB continuing review date. Subsequently, each protocol will be reviewed as close to annually as the quarterly meeting schedule permits or more frequently as may be required by the SMC. For initial and subsequent reviews, protocols will not be reviewed if there is no accrual within the review period. Written outcome letters will be generated in response to the monitoring activities and submitted to the PI and Clinical Director or Deputy Clinical Director, CCR, NCI.

8 STATISTICAL CONSIDERATIONS

8.1 STATISTICAL HYPOTHESIS

8.1.1 Primary Efficacy Endpoints

- Determine the clinical response rate in patients with metastatic melanoma, gastrointestinal, or genitourinary cancers who receive NCI-4650.
- Determine the safety of NCI-4650 in patients with metastatic melanoma, gastrointestinal, or genitourinary cancer.

8.1.2 Secondary Efficacy Endpoint

• Determine whether administration of NCI-4650, a mRNA-based, PCV presenting immunogenic neoantigens, can increase the quantity and quality of circulating antigen-specific T-cells in patients with solid tumors.

8.2 SAMPLE SIZE DETERMINATION

The study will be conducted using a phase I dose escalation followed by a phase II Simon minimax design in two cohorts: Cohort 2a, patients with melanoma and Cohort 2b, patients with gastrointestinal or genitourinary cancer.

Following dose escalation, the objective will be to determine if NCI-4650, given at the MTD, is associated with a clinical response rate that can rule out 5% (p0=0.05) in favor of a modest 20% PR+CR rate (p1=0.20) in each of the two cohorts in Phase II.

For each cohort in the Phase II portion of this study, using a two-stage Simon minimax design, with alpha=0.10 (10% probability of accepting a poor therapy) and beta=0.20 (20% probability of rejecting a good therapy), initially 12 evaluable patients will be enrolled. If 0 of the first 12 evaluable patients experience a clinical response, then no further patients will be enrolled in that cohort. If 1 or more of the first 12 evaluable patients enrolled have a clinical response, then accrual will continue until a total of 21 evaluable patients have been enrolled in that cohort. As it may take several weeks to determine if a patient has experienced a clinical response, a temporary pause of up to 6 months in the accrual to the trial may be necessary to ensure that enrollment to the second stage is warranted. If 1-2 of the 21 evaluable patients have a clinical response, then this will be considered inadequate for further investigation. If 3 or more of the 21 evaluable patients have a clinical response, then this will indicate that this strategy provides a new approach that may be worthy of further consideration in that cohort. Under the null hypothesis (10% response rate), the probability of early termination per cohort is 54.0%.

The dose escalation portion of the study may require 6 patients per dose level. For purposes of sample size estimation, we will assume that as few as 12 and no more than 18 patients will be

required to perform the initial safety evaluation. In order to complete the dose escalation phase and Phase II, a total of up to 18+46 =64 patients may be required (allowing up to 2 inevaluable patients per Phase II cohort). Up to 6 patients enrolled at the MTD will count towards the accrual in the Phase II portion of the trial if they are evaluable for response and if they would be fully eligible for enrollment in the Phase II portion of the trial. Provided that about 2-3 patients per month will be able to be enrolled onto this trial, approximately 2-3 years may be needed to accrue the maximum number of required patients. However, as adequate responses to proceed to the second stage of accrual may not occur, the trial may end up accruing many fewer patients.

8.3 POPULATIONS FOR ANALYSES

8.3.1 Evaluable for Toxicity

All patients will be evaluable for toxicity from the time of their first mRNA vaccine dose.

8.3.2 Evaluable for Objective Response

Only those patients who have measurable disease present at baseline, have received at least one course of therapy, and have had their disease re-evaluated will be considered evaluable for response. These patients will have their response classified according to the definitions stated in Section **6.3.3**.

8.3.3 Evaluable for Non-Target Disease Response

Patients who have lesions present at baseline that are evaluable but do not meet the definitions of measurable disease, have received at least one course of therapy, and have had their disease reevaluated will be considered evaluable for non-target disease. The response assessment is based on the presence, absence, or unequivocal progression of the lesions.

8.4 STATISTICAL ANALYSES

8.4.1 General Approach

In the Phase I cohort, the toxicities experienced by patients at each dose level will be reported per dose level. In the two Phase II cohorts, clinical responses will be determined and the fraction with a clinical response will be reported, along with confidence intervals.

8.4.2 Analysis of the Primary Efficacy Endpoints

In the Phase I cohort, the toxicities experienced by patients at each dose level will be reported per dose level. The grade of the toxicity as well as the type of toxicity will be tabulated per dose level.

In the Phase II cohorts, the fraction of patients who experience a clinical response in each cohort will be reported along with 80% and 95% two-sided confidence intervals.

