3.6 POST-TREATMENT (FOLLOW-UP) EVALUATIONS

3.6.1 First Follow-up Evaluation

All patients (unless the patient receives a second course of treatment) will return to the NIH Clinical Center for their first follow-up evaluation on day 56 (\pm 5 days), which is approximately two weeks after the fourth vaccination. If a patient receives a second course of four vaccines, the first follow-up evaluation will be two weeks (\pm 5 days) after the eighth vaccination.

At the first follow-up evaluation, patients will undergo:

- Physical examination, including ECOG (see Appendix B)
- Weight and vital signs
- Toxicity assessment, including a review of systems
- CBC w/differential
- Acute Care Panel (sodium, potassium, chloride, bicarbonate, creatinine, glucose, BUN), Hepatic Panel (alkaline phosphatase, AST, ALT, total bilirubin, direct bilirubin), Mineral Panel (albumin, calcium, magnesium, phosphorus), Uric acid, Creatinine kinase, Lactate dehydrogenase, Total protein
- Lymphocyte phenotyping (TBNK)
- β-HCG pregnancy test (serum or urine) on all women of child-bearing potential
- Research samples, as described in Section **5.3**. Approximately 72 mL of blood will be obtained. PBMC will be cryopreserved so that immunologic testing may be performed. This will be performed on protocol 03-C-0277.
- Imaging studies as performed at baseline to determine tumor response. If clinically indicated, other scans or x-rays may be performed, e.g. brain MRI, bone scan.
- A 5-liter apheresis may be performed. If the patient is unable to undergo apheresis, approximately 96 mL of blood may be obtained. This will be performed on protocol 03-C-0277.

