3.8.2 Off-Study Criteria

Patients will be taken off-study for the following:

- Vaccine does not meet CoA requirements
- Completion of study follow-up period
- Progression of disease
- Patients begins a new therapy for their cancer
- Patient requests to be withdrawn from the study
- Significant noncompliance
- Investigator discretion
- Patient lost to follow-up
- Patients who require the use of any medications listed in Section 4 for clinical management.
- Death

All patients will be co-enrolled on protocol 09-C-0161. Patients who are taken off-study for progressive disease or study closure on the treatment protocol will be followed on protocol 09-C-0161.

Once a subject is taken off-study, no further data can be collected on this treatment protocol.

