6 DATA COLLECTION AND EVALUATION

6.1 DATA COLLECTION

The PI will be responsible for overseeing entry of data into an in-house password-protected electronic system (C3D) and ensuring data accuracy, consistency and timeliness. The PI, associate investigators (AI), research nurses, and/or a contracted data manager will assist with the data management efforts. All data obtained during the conduct of the protocol will be kept in secure network drives or in approved alternative sites that comply with NIH security standards.

Primary and final analyzed data will have identifiers so that research data can be attributed to an individual human subject participant. Data will be entered into the NCI CCR C3D database.

All AEs, including clinically significant abnormal findings on laboratory evaluations, regardless of severity, will be followed until return to baseline or stabilization of event. Patients will be followed for AEs from the time the patient receives the first mRNA vaccine dose to the time of the second follow-up evaluation, or until off-study, whichever comes first.

An abnormal laboratory value will be recorded in the database as an AE **only** if the laboratory abnormality is characterized by any of the following:

- Results in discontinuation from the study
- Is associated with clinical signs or symptoms
- Requires treatment or any other therapeutic intervention
- Is associated with death or another serious adverse event, including hospitalization
- Is judged by the investigator to be of significant clinical impact
- If any abnormal laboratory result is considered clinically significant, the investigator will provide details about the action taken with respect to the test drug and about the patient's outcome.

All AEs must be recorded on the AE case report form unless otherwise noted below in Section **6.1.1**.

End of study procedures: Data will be stored according to HHS and FDA regulations, and NIH Intramural Records Retention Schedule as applicable.

Loss or destruction of data: Should we become aware that a major breach in our plan to protect subject confidentiality and trial data has occurred, the NIH Intramural IRB will be notified.

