8.4.4 Safety Analyses

Safety will be monitored by identifying the type and severity of any adverse events. The fraction of patients who experience a DLT will be identified at a given dose level, with information reported about the number and grade of each type of DLT identified.

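### The Phase I toxicity table per dose level pools patients observed over four and over eight vaccinations, so its entries reflect second-course uptake as well as dose

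*Combined protocol and SAP*

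**What the plan says.** Safety is one of the two primary objectives (1.1.1, repeated in 8.1.1). Sections 8.4.1 and 8.4.2 report Phase I toxicities by dose level, and 8.4.2 adds: "The grade of the toxicity as well as the type of toxicity will be tabulated per dose level". Section 8.4.4 says "Safety will be monitored by identifying the type and severity of any adverse events" and also reports the fraction of patients with a DLT at each dose level. On the population, 8.3.1 says: "All patients will be evaluable for toxicity from the time of their first mRNA vaccine dose". It gives no end point.

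The end of observation is in 6.1: "Patients will be followed for AEs from the time the patient receives the first mRNA vaccine dose to the time of the second follow-up evaluation", with the limit "or until off-study, whichever comes first". Section 3.6.1 sets the first follow-up visit at Day 56 after one course. For two courses the timing moves: "If a patient receives a second course of four vaccines, the first follow-up evaluation will be two weeks" after the eighth vaccination. Section 3.6.2 puts the second follow-up visit one month after the first.

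Under 3.1.3, the second course has four more vaccinations at the same dose. It starts about four weeks (plus or minus two) after the fourth vaccination. It is open to patients whose blood shows a 3-fold rise in neoantigen-specific T-cells or newly detectable reactivity.

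**The concern.** The table that describes a primary objective has no stated exposure. A patient with two courses receives twice the vaccinations and is followed for nearly twice as long as a patient with one, yet both enter the same dose-level row. Which patients have the longer exposure is decided by an immune result obtained after treatment began, and that result may itself vary with dose.

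At stake is how the table can be read. If more patients at one level go on to a second course, that level can show more toxicity at the same risk per vaccination. Even with equal uptake, a pooled entry describes neither a four-vaccination nor an eight-vaccination exposure. Readers have reason to look past DLTs: 3.1.5 says that finding the MTD is not the aim, because lower doses may bring benefit. Section 3.1.6 treats cumulative toxicity as a matter that needs a safety margin.

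**Working it through.** **Inputs from the documents**
- Course 1 vaccinations on Days 0, 14, 28 and 42 (3.1.5, 3.3).
- First follow-up 14 days after the last vaccination; second follow-up one month later (3.6.1, 3.6.2).
- Dose 5 given 28 days after dose 4, allowed range 14 to 42 days (3.1.3).

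**Assumptions.** One month is 30 days, and the two-week interval also holds in the second course.

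**The plan's own figure.** First follow-up after one course: 42 + 14 = Day 56. This matches 3.6.1. The documents do not state the later days below.

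**Length of the adverse-event window**
- One course: 56 + 30 = Day 86 (Day 84 to 87 for a month of 28 to 31 days).
- Two courses: dose 5 at 42 + 28 = Day 70; dose 8 at 70 + 42 = Day 112; first follow-up at 112 + 14 = Day 126; second follow-up at 126 + 30 = Day 156.
- With a gap of 14 or 42 days in place of 28, Day 156 becomes Day 142 or Day 170.
- Ratios: 156/86 = 1.81 in days and 8/4 = 2.0 in vaccinations.

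These are nominal maxima. Going off-study ends collection sooner, and "Progression of disease" is one of the triggers in 3.8.2.

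**Illustration of size.** The documents give no risk per vaccination, so q is assumed, equal at all doses and independent between vaccinations. The chance of at least one event is 1 − (1 − q)^k, with k = 4 or 8.

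| q | k = 4 | k = 8 | Difference |
|---|---|---|---|
| 0.05 | 18.5% | 33.7% | 15 points |
| 0.10 | 34.4% | 57.0% | 23 points |
| 0.20 | 59.0% | 83.2% | 24 points |

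Real levels will be mixed. For q = 0.10 and three patients at a level, the expected share affected is 34.4%, 41.9%, 49.4% or 57.0% when 0, 1, 2 or 3 of them have a second course.

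**Does a dose effect still show?** Yes. Doubling q from 0.05 to 0.10 raises the four-vaccination figure from 18.5% to 34.4% and the eight-vaccination figure from 33.7% to 57.0%. But eight vaccinations at q = 0.05 (33.7%) look almost the same as four at q = 0.10 (34.4%). The pooled table cannot separate the two.

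**Does the DLT fraction cover the gap?** The DLT window is 21 days after the first vaccination (3.1.4). It is the same for every patient and closes before any second course. It nominally spans only the vaccinations on Days 0 and 14, and it counts only related events of grade 3 or higher, with listed exceptions. Lower-grade events, and events after later vaccinations, reach the reader only through the toxicity table.

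**The case against.** The strongest reply is that this is a small descriptive table that drives no decision. Section 8.4.2 names no rate, no test and no comparison between levels. The only per-level fraction in the safety analysis is the DLT fraction, whose window is common to all patients, and that governs escalation, the MTD and the DLT-based halts in 3.2. This part of the objection stands and limits the severity.

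The percentages above can also be read too strongly. They set a level with no second courses against a level with all second courses, and they assume independence. If the same patients tend to react each time, the rise from four to eight vaccinations is smaller. Under 3.8.1, vaccine toxicity of grade 3 or 4 outside the listed exceptions ends treatment, so patients with such events receive no further doses. Levels are small: 3.1.5 describes two patients at Level 2, then three planned at Level 3 unless a DLT occurs, with six as the expanded size. At q = 0.10 the difference of 22.6 points is 0.7 of a patient in three (3 × 0.226) or 1.4 in six (6 × 0.226).

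A reader might infer that the table moves with second-course uptake instead of dose. The documents do not support that. The second course uses the same dose, so each event stays at its correct level and a true dose effect still appears. Distortion between levels needs uptake to differ by level, which the documents neither state nor exclude.

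It can also be said that cumulative toxicity of the regimen as offered is a legitimate summary, and that 3.1.3 already dates each course. The first half is right, and the cumulative table should stay. The second half does not solve the problem. By those dates the first course ends at the first post-treatment evaluation (nominally Day 56) for a one-course patient, but at dose 5 (nominally Day 70, range 56 to 84) for a two-course patient. Splitting by those dates would still give unequal windows.

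**Conclusion.** The point holds in limited form. As planned, the Phase I toxicity table per dose level pools 4 vaccinations observed to about Day 86 with 8 observed to about Day 156 (142 to 170), in both cases less if the patient goes off-study. Because a post-baseline T-cell response opens the second course, entries reflect uptake as well as dose, and comparison between levels can be distorted if uptake differs by level.

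The exposure ratios (1.8 in days, 2.0 in vaccinations) follow from the visit schedule with a 30-day month. The differences of 15 to 24 points are an upper-end illustration under assumed, independent risks of 5% to 20% per vaccination. They are not an expected bias. The DLT fraction, escalation and the DLT-based stopping rules are not affected. This is a cheap improvement of low severity.

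**What to change.** In 8.4.2, specify the following for the Phase I cohort:

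1. A first-course table of toxicity grade and type per dose level, with one cut-off for all patients: onset from dose 1 up to 14 days after the last first-course vaccination (nominally Day 56) and before any dose 5. The earliest nominal dose 5 is also Day 56 (42 + 14), so two-course patients nominally lose no observation time under this rule.
2. A separate table of events from dose 5 onward, with the patients who started the second course as denominator.
3. The cumulative table over the full adverse-event window, kept as planned.
4. Vaccinations given and days observed, shown per dose level beside these tables.

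The cost is a few lines of SAP wording and one extra small table, all from data already collected. Second-course counts will be sparse. Events after the first-course cut-off but before dose 5, or after the cut-off in one-course patients, will appear only in the cumulative table.
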